### **7.7.1. Management of Patients with Gastrointestinal Symptoms**

In the Phase 2 program, the most commonly reported treatment-emergent AEs (TEAEs) for patients receiving LY3298176 were nausea, vomiting, and diarrhea.

The LY3298176 dose escalation scheme has been designed to minimize the development of intolerable GI symptoms. The escalation period is considered to be 24 weeks, which allows 20 weeks to escalate to 15 mg and additional 4 weeks to reach steady state. During the dose escalation period, every effort should be made by the investigator to be able to escalate and maintain patients on the corresponding study drug dosage.

To mitigate GI symptoms and manage patients with intolerable GI AEs, the investigator should:

- Advise patients to eat smaller meals, for example, splitting 3 daily meals into 4 or more smaller meals, and to stop eating when they feel full.
- Prescribe symptomatic medication (for example, anti-emetic or anti-diarrheal medication) per local country availability and individual patient needs. Use of symptomatic medication should be captured as concomitant medication in the eCRF.
- Temporarily interrupt LY3298176 (omit 1 dose, the patient will take 3 of 4 doses at that dose level). The data related to temporary interruption of study treatment should be documented in source documents and entered on the eCRF.
- After the interruption, restart at the same dose with the patient taking medication to alleviate their GI symptoms (Section 8.1.2).

If intolerable GI symptoms or events persist despite the above measures, the investigator may decide to continue treatment at a lower, tolerated maintenance dose of LY3298176 (5 mg or 10 mg).

- Patients at 5 mg or lower will be discontinued from LY3298176.
- Patients at 7.5 mg or 10 mg will decrease the dose to 5 mg.
- Patients at 12.5 mg or 15 mg will decrease the dose to 10 mg.

If de-escalation of the LY3298176 dose is necessary, the investigator will use the IWRS to receive the appropriate LY3298176 dispensing information. If de-escalation is needed between scheduled visits, the IWRS will have unscheduled visits (for example, Visit 13a) dedicated to provide dispensing information for patients whose dose has been de-escalated. Those patients, who have their dose de-escalated, will not be escalated again. The dose can be de-escalated only once. After that, the patients will have to discontinue LY3298176 if intolerable GI AE persists. Please see the Manual of Operations for more detailed instructions.

If intolerable persistent GI symptoms occur after Week 24, the investigator should take the above measures to keep the patient on study treatment. However, after the escalation period (Week 24), dose decreases will not be allowed.

## **7.8. Treatment after the End of the Study**

### **7.8.1. Treatment after Study Completion**

Study completion will occur after all patients complete the follow-up visit. Investigators will continue to follow Schedule of Activities (Section 2) for all patients until notified by Lilly that study completion has occurred.

LY3298176 will not be made available after conclusion of the study to patients.

### **7.8.2. Special Treatment Considerations**

Investigators will be trained on how to apply decision criteria for the timing and method of intervention in patients who do not reach glycemic targets during the treatment period. An additional therapeutic intervention should be considered for patients with persistent hyperglycemia as described in Section 9.2.2.2.

## 8. Discontinuation Criteria

### 8.1. Discontinuation from Study Treatment

#### 8.1.1. *Permanent Discontinuation from Study Treatment*

Possible reasons leading to permanent discontinuation of investigational product:

- **Patient Decision**
  - The patient requests to discontinue investigational product.
- **Discontinuation due to a hepatic event or liver test abnormality.** Patients who are discontinued from investigational product due to a hepatic event or liver test abnormality should have additional hepatic safety data collected via the eCRF.

Discontinuation of the investigational product for abnormal liver tests **should be** considered by the investigator when a patient meets one of the following conditions after consultation with the Lilly-designated medical monitor:

- ALT or aspartate aminotransferase (AST) >8X ULN
- ALT or AST >5X ULN for more than 2 weeks
- ALT or AST >3X ULN and total bilirubin level (TBL) >2X ULN or international normalized ratio (INR) >1.5
- ALT or AST >3X ULN with the appearance of fatigue, nausea, vomiting, right upper-quadrant pain or tenderness, fever, rash, and/or eosinophilia (>5%)
- alkaline phosphatase (ALP) >3X ULN
- ALP >2.5X ULN and TBL >2X ULN
- ALP >2.5X ULN with the appearance of fatigue, nausea, vomiting, right quadrant pain or tenderness, fever, rash, and/or eosinophilia (>5%)

In addition, patients will be discontinued from the investigational product in the following circumstances:

- If a patient is inadvertently enrolled and it is determined that continued treatment with study drug would not be medically appropriate, see Section 8.1.3
- Acute or chronic pancreatitis
- If a patient is diagnosed with MTC after randomization, or has a postrandomization calcitonin value  $\geq 35$  ng/L that has increased at least 50% over baseline
- If a patient is diagnosed with an active or untreated malignancy (other than basal or squamous cell skin cancer, in situ carcinomas of the cervix, or in situ prostate cancer) after randomization
- Any significant study drug-related hypersensitivity reaction

- Any other TEAE, SAE, or clinically significant laboratory value for which the investigator believes that permanent study drug discontinuation is the appropriate measure to be taken
- If female patient becomes pregnant
- If a patient is diagnosed with T1DM

Patients who stop the study drug permanently will receive another glucose-lowering intervention (Section 7.4.2) and will continue participating in the trial according to the protocol to collect all planned efficacy and safety measurements.

Patients discontinuing from the investigational product prematurely for any reason should complete AE and other follow-up procedures per Section 2 Schedule of Activities, Section 9.2 Adverse Event, and Section 9.4 Safety of this protocol.

### **8.1.2. Temporary Discontinuation from Study Treatment**

In certain situations after randomization, the investigator may need to temporarily interrupt study drug. Every effort should be made by the investigator to maintain patients on study drug and to restart study drug after any temporary interruption, as soon as it is safe to do so.

For patients assigned to LY3298176:

- If the number of doses missed is  $\leq 2$ , the treatment can be restarted at the same dose, if the drug was well tolerated prior to discontinuation.
- If the number of missed doses is  $\geq 3$ , then the treatment should be restarted at 5 mg irrespective of the dose the patient was receiving before the interruption and subsequently escalated as required by protocol (See Manual of Operations for further details).

If study drug interruption is due to an AE, the event is to be documented and followed according to the procedures in Section 9.2 of this protocol. If the study drug interruption is due to intolerable persistent GI AE (for example, nausea, vomiting, or diarrhea), the patients should be treated as suggested in Section 7.7.1.

The data related to temporary interruption of study treatment will be documented in source documents and entered on the eCRF.

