#### *Postrandomization period (end of Visit 3 to Visit 21):*

The starting dose of LY3298176 will be 2.5 mg QW for 4 weeks, followed by an increase to 5 mg QW, for the duration of the study in the 5 mg group. For the 10-mg group, the starting dose of LY3298176 will be 2.5 mg QW for 4 weeks, then the dose will be increased by 2.5 mg every 4 weeks (2.5 to 5 to 7.5 to 10 mg) until the 10-mg dose is reached and maintained for the duration of the study. For the 15-mg group, the starting dose of LY3298176 will be 2.5 mg QW

for 4 weeks, then the dose will be increased by 2.5 mg every 4 weeks (2.5 to 5 to 7.5 to 10 to 12.5 to 15 mg) until the 15-mg dose is reached and maintained for the duration of the study.

The initial dose of insulin degludec will be 10 IU/day ideally at bedtime, titrated to a FBG <90 mg/dL, following a TTT algorithm (Philis-Tsimikas et al. 2013; Pan et al. 2016; Aroda et al. 2016) (see Section 7.2.1.2, Table GPGH.4).

Most of the insulin degludec titration should occur during the first 16 weeks of the study, followed by a 36-week maintenance period. The maintenance period is defined as a part of the titration period when the insulin degludec dose is expected to be stable and optimized (Weeks 16-52 [Visits 15-21]).

During the first 8 weeks, the insulin degludec dose adjustment will be determined by the investigator in discussion with the patient and this time will be used as preparation and training for implementation of the patient self-titration according to the TTT algorithm (Section 7.2.1.2, Table GPGH.4). After Week 8, the decision of the titration will be made and implemented by the patient in a weekly manner. Between Week 8 and Week 16, investigators or study site personnel will contact the patient every 2 weeks (office or telephone visit) and will review the insulin dose adjustment made by the patient at each of these visits. Investigators may perform additional telephone visits if necessary, or perform additional office visits if the investigator deems additional training is necessary.

During the treatment period, office visits will occur weekly or every other week during the first 16 weeks, and thereafter, every 4 to 8 weeks to enable the site to properly monitor patients' usage of the TTT algorithm.

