### **5.5. Justification for Dose**

LY3298176 doses of 5 mg, 10 mg, and 15 mg administered subcutaneously QW will be evaluated in this study.

These doses and associated escalation schemes were selected based on assessment of safety, efficacy (glycemic and weight loss benefit), and GI tolerability data followed by exposure response modeling of data in patients with T2DM in Phases 1 and 2 studies. Dosing algorithms starting at a low dose of 2.5 mg accompanied by dose escalation of 2.5 mg increments every 4-week would permit time for development of tolerance to GI events and are predicted to minimize GI tolerability concerns.

The maximum proposed dose of 15 mg maintains an exposure multiple of 1.6 to 2.4 to the no-observed adverse effect level doses in 6-month monkey and rat toxicology studies.

The selected dose and escalation scheme would enable further evaluation of benefit/risk considerations for 5 mg, 10 mg, and 15 mg doses of LY3298176.

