### 7.4. Dosage Modification

#### 7.4.1. Study Drugs

Details about dose administration of LY3298176 during the study are described in Sections 7.2.1 and 8.1.2.

Insulin degludec will be adjusted according to the TTT method (see Section 7.2.1.2 Table GPGH.4).

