#### **9.2.2.7. Hypersensitivity Events**

All allergic or hypersensitivity reactions will be reported by the investigator as either AEs or, if any serious criterion is met, as SAEs. Additional data, such as type of reaction and treatment received, will be collected on any AEs or SAEs that the investigator deems related to study drug(s) via a CRF created for this purpose. Additional samples should also be collected as outlined in Section 9.4.3. Study drug(s) should be temporarily interrupted in any individual suspected of having a severe or serious allergic reaction to study drug(s). Study drug(s) may be restarted when/if it is safe to do so, in the opinion of the investigator. If study drug(s) is permanently discontinued, the patient will receive another glucose-lowering treatment, judged by the investigator to be appropriate based on the patient's clinical status, and will continue in the trial to collect all planned efficacy and safety measurements.

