### **9.4.4. Immunogenicity Assessments**

Where local regulations and ERBs allow, blood samples for immunogenicity testing will be collected to determine antibody production against LY3298176 as specified in the Schedule of Activities (Section [2](#)).

At the visits and times specified in the Schedule of Activities (Section [2](#)), venous blood samples will be collected to determine antibody production against the LY3298176. To interpret the results of immunogenicity, a PK sample will be collected at the same time points as the immunogenicity sample. All samples for immunogenicity should be taken predose when applicable and possible. In the event of drug hypersensitivity reactions (immediate or non-immediate), additional samples will be collected (including ADA, PK, and exploratory immune safety sample) as close to the onset of the event as possible, at the resolution of the event, and 30 days following the onset of the event. Instructions for the collection and handling of blood samples will be provided by the sponsor. Sample collected at Visit 801 will assess immunogenicity at washout of LY3298176 (5 half-lives post end of treatment).

Treatment-emergent ADAs are defined in Section [10.3.5](#).

Samples with LY3298176 ADA detected will be titered and evaluated for their ability to neutralize the activity of assigned treatment (LY3298176-neutralizing antibodies). Samples with LY3298176 ADA detected will also be tested for cross-reactive binding to native GIP and GLP-1, and, if such is detected, then for neutralizing antibodies against native GIP and GLP-1, respectively.

Samples will be retained for a maximum of 15 years after the last patient visit, or for a shorter period if local regulations and ethical review boards (ERBs) allow, at a facility selected by the sponsor. The duration allows the sponsor to respond to future regulatory requests related to LY3298176. Any samples remaining after 15 years will be destroyed.

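### After three or more missed doses, the fixed 5-mg restart doubles the dose for patients still on 2.5 mg and skips the rest of their low-dose step

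*Protocol*

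**What the plan says.** All three LY3298176 arms begin alike. Protocol Section 5.1 states: "The starting dose of LY3298176 will be 2.5 mg QW for 4 weeks". The dose then goes to 5 mg and, in the 10-mg and 15-mg arms, rises by 2.5 mg every 4 weeks. Section 5.5 gives the reason for the slow start: "Dosing algorithms starting at a low dose of 2.5 mg accompanied by dose escalation of 2.5 mg increments every 4-week would permit time" for tolerance to gastrointestinal events to develop.

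Section 7.4.1 says where the dosing rules are: "Details about dose administration of LY3298176 during the study are described in Sections 7.2.1 and 8.1.2". Section 7.2.1.1 deals only with a single late or missed dose, so Section 8.1.2 holds the only rule for the restart dose. It has two branches:

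- Two or fewer missed doses: "the treatment can be restarted at the same dose, if the drug was well tolerated prior to discontinuation".
- Three or more missed doses: "then the treatment should be restarted at 5 mg irrespective of the dose the patient was receiving before the interruption", followed by escalation under the protocol. The Manual of Operations is cited for further details. It is not among the documents.

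Section 9.2.2.7 interrupts study drug when a severe or serious allergic reaction is suspected, and then says: "Study drug(s) may be restarted when/if it is safe to do so, in the opinion of the investigator". It gives no restart dose, so Section 8.1.2 applies. Section 8.1.1 lists a reason for permanent discontinuation that limits this group: "Any significant study drug-related hypersensitivity reaction".

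**The concern.** Reducing the dose after a long gap is sensible when the patient comes from a high dose. At 2.5 mg the same sentence works the other way. A patient who misses two doses may resume 2.5 mg, on condition that it was well tolerated. A patient who misses three goes to 5 mg, and that branch carries no tolerability condition. The longer gap brings the higher dose and the weaker safeguard.

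What is at stake is gastrointestinal tolerance in patients who have had little of the drug. They lose part or most of the introductory step and meet 5 mg almost drug-free. In the 5-mg arm, 5 mg is already the full maintenance dose. An investigator who would rather resume at 2.5 mg has to depart from the protocol text to do so.

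**Working it through.** **Inputs.** Weekly dosing; 2.5 mg at Weeks 0 to 3, then steps of 4 weeks (Section 5.1); 5-mg restart after three or more missed doses (Section 8.1.2); de-escalation not allowed after Week 24 (Section 7.7.1).

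**Direction of the rule.** Restart dose divided by prior dose:

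| Prior dose (mg) | 2.5 | 5 | 7.5 | 10 | 12.5 | 15 |
|---|---|---|---|---|---|---|
| 5 mg / prior dose | 2.0 | 1.0 | 0.67 | 0.50 | 0.40 | 0.33 |

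The rule lowers four levels, keeps one and raises one.

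**Time off drug.** Three missed weekly doses put 4 × 7 = 28 days between doses. Section 9.4.4 ties the follow-up visit, 4 weeks after the end of treatment, to washout: "Sample collected at Visit 801 will assess immunogenicity at washout of LY3298176 (5 half-lives post end of treatment". Counting from the last dose, the implied half-life is 28/5 = 5.6 days, and 0.5^5 = 3.1% remains after 28 days. If the last dose came 7 days before the end-of-treatment visit, the half-life is 35/5 = 7 days, and 0.5^4 = 6.25% remains. This assumes first-order elimination.

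**Time to 15 mg.** The uninterrupted schedule takes 5 steps × 4 weeks = 20 weeks, which matches the 20 weeks given in Section 7.7.1. Now let a patient take n doses of 2.5 mg (Weeks 0 to n − 1) and then miss m doses, so that restart falls at Week n + m.

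- Present rule: 15 mg is reached at Week n + m + 4 × 4 = n + m + 16.
- Completing the 4 − n untaken 2.5-mg doses first: Week n + m + (4 − n) + 16 = m + 20.

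With exactly three missed doses (m = 3):

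| 2.5-mg doses taken | Restart | 15 mg, present rule | 15 mg, step completed | Delay (weeks) |
|---|---|---|---|---|
| 1 | Week 4 | Week 20 | Week 23 | 3 |
| 2 | Week 5 | Week 21 | Week 23 | 2 |
| 3 | Week 6 | Week 22 | Week 23 | 1 |
| 4 | Week 7 | Week 23 | Week 23 | 0 |

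A patient in the last row held for a suspected allergic reaction, and given one further 2.5-mg dose before escalating, reaches 15 mg at Week 24.

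Longer gaps move everything later. With m = 5 the completed step gives Week 25, and the present rule gives Week 22 (n = 1) to Week 25 (n = 4).

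**The case against.** The strongest reply is that 5 mg is never ahead of the calendar. The earliest restart under this branch is Week 4, when every arm is due to take 5 mg anyway, so the doubling is the ordinary first escalation. Section 7.7.1 also accepts three of four doses at a level when one is omitted for gastrointestinal symptoms. Section 3.2 reports repeated 5-mg weekly dosing in patients with type 2 diabetes in Phase 1. It says that the 10-mg and 15-mg doses in the 26-week Phase 2 study were reached by titration, which suggests that 5 mg was not. All of this stands, and it limits the likely harm. It does not answer the point on exposure: one dose of four is well short of three of four, and Section 5.5 relies on time spent at the low dose. Section 3.2 also gives 5 mg as the maximum tolerated dose in the single-ascending-dose part of Phase 1.

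A second reply is that washout proves too much, since a patient coming from 15 mg has the same fraction left and also restarts at 5 mg. That is right, so washout alone is not the argument. The difference is that the 15-mg patient has been through the low steps and resumes at a third of a dose already taken.

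A reader might infer something stronger: that the protocol doubles the dose after a severe allergic reaction. The documents do not support that. Section 8.1.1 permanently stops any significant drug-related reaction, and Section 9.2.2.7 permits restart only if the investigator considers it safe. Nothing in the documents shows a different allergic risk at 2.5 mg and 5 mg. Nor do the two sections conflict, since one deals with suspicion and the other with a significant drug-related reaction.

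Finally, the Manual of Operations may give more detail. It cannot be checked here, and the protocol sentence is unconditional on the prior dose.

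**Conclusion.** The point holds as a gap in the general restart rule. For patients on 2.5 mg, and only for them, three or more missed doses lead to a restart at twice the prior dose, at least 28 days after the last dose, with as few as one of four introductory doses taken. Patients held for a suspected allergic reaction and then cleared are a small part of this group.

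The documents give no rate of interruption or of such reactions, so the number affected cannot be computed; it is probably small. All 3 × 355 = 1065 of the 1420 planned patients (75%) pass through 2.5 mg. A reader might take that as the number at risk, but it counts everyone who ever takes the dose, not those who miss three doses while on it. The analysis sets in SAP Table GPGH.6.1 do not depend on the restart dose, so no analysis set changes.

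The conclusion assumes that the Manual of Operations does not override the protocol text. The residual-drug figures (about 3% to 6%) rest on the protocol's five-half-life statement. This is a cheap improvement, not a defect that threatens the trial.

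**What to change.** 1. In Section 8.1.2, reword the second branch: *After three or more missed doses, restart at 5 mg. Exception: a patient whose last dose was 2.5 mg and who has not completed four 2.5-mg doses restarts at 2.5 mg, completes the remaining 2.5-mg doses, and then escalates on the protocol schedule.* Tying the exception to the last dose keeps it from reaching a patient on a higher level who once omitted a 2.5-mg dose.

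2. In Section 9.2.2.7, add: *LY3298176 must not be restarted at a dose higher than the last dose taken before the reaction.* A patient who had already taken all four 2.5-mg doses then takes at least one more before escalating. Section 8.1.1 stays as it is.

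**Cost.** The change needs two wording edits and one IWRS dispensing rule for a 2.5-mg restart. Change 1 delays affected patients by 1 to 3 weeks.

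In the 15-mg arm with exactly three missed doses, 15 mg is reached at Week 23, or Week 24 in the extra-dose case under change 2, so the Week 24 limit on de-escalation is not passed. The time at 15 mg within that limit does shrink: 24 − 23 = 1 week, against 24 − 20 = 4 weeks for a one-dose patient under the present rule, and none in the Week 24 case. Longer gaps can pass Week 24, as they already can now, so the sponsor should say how the limit applies to these patients.

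Repeating the full 4 weeks at 2.5 mg is not recommended. A patient restarting at Week 7 would reach 15 mg only at Week 7 + 5 × 4 = 27.

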### **8.1.3. Discontinuation of Inadvertently Enrolled Patients**

If the sponsor or investigator identify a patient who did not meet enrollment criteria and was inadvertently enrolled, then the patient should be discontinued from study treatment unless there are extenuating circumstances that make it medically necessary for the patient to continue on study treatment. If the investigator and the sponsor clinical research physician (CRP) agree it is medically appropriate to continue, the investigator must obtain documented approval from the sponsor CRP to allow the inadvertently enrolled patient to continue in the study with or without treatment with investigational product. Safety follow-up is as outlined in Section 2 (Schedule of Activities), Section 9.2 (Adverse Events), and Section 9.4 (Safety) of the protocol.

